12.4.4 Sensitivity and Supportive analyses

Sensitivity analyses

A sensitivity analysis will assess PFS events if a patient has disease progression or death regardless of whether the patient had missing scheduled visits, treatment discontinuation for toxicity, or new anticancer treatment started without progression.

As sensitivity analyses performed in the FAS, the hazard ratio and 95% confidence interval for PFS per blinded independent central review will be obtained from an unstratified and covariate unadjusted Cox model, except when the primary analysis is unstratified, see Section 12.4.2.

Further sensitivity analyses will be specified in the SAP.

Supportive analyses

As a supportive analysis, PFS as per local assessment will be analyzed using a stratified Cox model, with the same analysis conventions as the primary efficacy analysis, and the treatment effect will be summarized by the hazard ratio with its 95% confidence interval. Kaplan-Meier curves, medians and 95% confidence intervals of the medians will be presented for each treatment group.

As supportive analyses performed in the FAS, the hazard ratio and 95% confidence interval for PFS per blinded independent central review will be obtained from:

• A stratified and covariate adjusted Cox model including as covariates the following: ALP, Time since Diagnosis, Time since Metastasis. The final list of covariates to be included in the model will be provided in the SAP.

• Further supportive analyses will be specified in the SAP

These analyses will include Kaplan-Meier medians with their 95% confidence intervals, and hazard ratios and their 95% confidence intervals from stratified Cox models.

If the primary analysis is statistically significant, subgroup analyses to assess the homogeneity of the treatment effect across demographic and baseline disease characteristics will be performed. The subgroups will include the stratification factors (Grade and Site), Age, Gender, Race, Karnofsky score, Tumor burden at baseline, BMI. The subgroups will be further detailed in the SAP.

The number of subjects censored and reasons for censoring will be summarized by treatment group using descriptive statistics, presented separately for local review and blinded independent central review.

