2.5.1 Primary endpoint

The primary endpoint of the study is progression-free survival (PFS), defined as the time from the date of randomization to the date of the first documented progression or death due to any cause. PFS will be assessed via central review according to RECIST 1.1. The Full Analysis Set will be the primary analysis population and will include all data observed up to the cut-off date.

If a patient has not progressed or died by the analysis cut-off date, PFS will be censored at the date of the last adequate tumor evaluation date before the cut-off date.

PFS events documented after the initiation of new anti-neoplastic therapy (i.e., RECIST 1.1 documented disease progression per central review or death) will be censored for the primary analysis at the last adequate tumor assessment prior to start of the new therapy. A separate

sensitivity analysis will be conducted that considers such events as PFS events for the primary analysis provided central review of tumor assessments continues after initiation of new cancer therapy. Additional details regarding censoring rules and determination of date of last adequate tumor assessment are provided in [Section 2.5.3](#).

Discontinuation due to disease progression (collected on the 'End of Treatment' disposition page) without supporting objective evidence satisfying progression criteria per RECIST 1.1 will not be considered disease progression for PFS derivation. Clinical deterioration will not be considered as a qualifying event for progression in the primary analysis.

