2.5.4 Handling of missing values/censoring/discontinuations

This is an event-driven trial and the primary analysis for PFS will be performed after 99 PFS events have been documented based on central review of tumor assessments.

In the primary analysis, PFS will be censored at the date of the last adequate tumor assessment if no PFS event is observed prior to the analysis cut-off date.

Disease progressions (i.e., central review RECIST 1.1 documented disease progression) or deaths documented after the initiation of new anti-cancer therapy will not be counted as PFS events for the primary analysis.

The date of last adequate tumor assessment is the date of the last tumor assessment with overall response of CR, PR, or SD before an event or a censoring reason occurred. In this case, the last tumor evaluation date at that assessment will be used. If no post-baseline assessments are available (before an event or a censoring reason occurred) then the date of randomization will be used.

In particular, PFS will be censored at the last adequate tumor assessment if one of the following occurs: absence of event; the event occurred after two or more missing tumor assessments.

The term “missing adequate tumor assessment” is defined as a tumor assessment not performed or tumor assessment with overall response of “UNK”. The rule to determine number of missing tumor assessments is based on the time interval between the date of last adequate tumor assessment and the date of an event. If the interval is greater than twice the protocol-specified interval between the tumor assessments and 2 times the protocol-allowed time window around assessments, then the number of missing assessments will be 2 or more.

Note that according to the protocol the first tumor assessment should occur at 16 weeks, then the second tumor assessment should occur 8 weeks later, and then the frequency should be every 12 weeks thereafter. For patients who discontinue from treatment without PD due to central review, tumor assessments should be taken every 12 weeks starting from the last tumor assessment until documented disease progression for central review per RECIST 1.1. Exact time windows to take into account missing assessments for PFS event determination is further discussed in [Section 5.5](#).

Refer to [Table 2.5-1](#) for censoring and event date options and outcomes for primary PFS.

Table 2.5-1 Derivation of primary PFS

Situation	Options	Outcome

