A. No baseline assessment, or, No post baseline assessment	Date of randomization	Censored
B. Progression or death at or before next scheduled assessment	Date of progression (or death)	Progressed
C. Progression or death after exactly one missing assessment	Date of progression (or death)	Progressed
D. Progression or death after two or more missing assessments	Date of last adequate assessment prior to missed assessment	Censored
E. No progression (or death)	Date of last adequate assessment	Censored
F. Treatment discontinuation due to 'Disease progression' without documented progression, i.e., clinical progression based on investigator claim	Ignore clinical progression and follow situations above	As per above situations
G. Start of new anticancer therapy, cross-over to or re-treatment with Lutathera prior to protocol defined progression per central review	Primary analysis: Censor patient at last adequate tumor assessment prior to new anti-cancer therapy	Censored
H. Death before first PD assessment	Date of death	Event

In particular, for censoring reason G in [Table 2.5-1](#), new anticancer therapy is defined as one of the following:

- For new anti-cancer medications post-randomization:
 - Medications which are in the ATC2 class of Antineoplastic agents or
 - Medications which are in the ATC4 class of Various therapeutic radiopharmaceuticals

- Class of medications of Somatostatin and Analogues excluding Octreotide and Octreotide Acetate
- For new anti-cancer procedures post randomization:
 - Any radiotherapies
 - Procedures (including surgery) with indication of Underlying disease in Concomitant non-drug therapies and interventions eCRF page

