2.5.6 Supplementary analyses

As supplementary analyses, PFS as per local review will be analyzed using a stratified Cox model, with the same analysis conventions as the primary efficacy analysis, and the treatment effect will be summarized by the hazard ratio with its 95% confidence interval. Kaplan-Meier curves, medians and 95% confidence intervals of the medians will be presented for each treatment group.

In addition, the primary efficacy endpoint will be summarized based on the data obtained below to assess different censoring mechanisms. Kaplan-Meier estimate of median PFS along with 95% confidence intervals, and hazard ratio and corresponding 95% confidence interval obtained using the Cox proportional hazards model will be provided. No other inferential statistics will be provided.

- Using the primary analysis source (i.e., central review using RECIST 1.1 criteria) on the FAS and including events whenever they occur, even after two or missing tumor assessments. The rule to determine number of missing tumor assessments is based on

the time interval between the date of last adequate tumor assessment and the date of event (see [Section 5.5](#)). If the interval is greater than twice the protocol-specified interval between the tumor assessment and two times the protocol-allowed time window around assessments, then the number of missing assessments will be two or more. In the summary tables, this approach is referred to as ‘actual event PFS supplementary analysis’.

- Using the primary analysis source (i.e., central review using RECIST 1.1 criteria) on the FAS and backdating events that occurred after missing one or more tumor assessments (i.e., if progression/death is observed after one or more missing tumor assessments, it is considered as an event at the date of the next scheduled assessment following the last adequate tumor assessment. In the summary tables, this approach is referred to as ‘backdating PFS supplementary analysis’).
- Using the primary analysis source (i.e., central review using RECIST 1.1 criteria) on the FAS and including events that occur after the start of new antineoplastic therapy if no PFS event is observed prior to the start of new antineoplastic therapy (not counting biopsies as a new antineoplastic surgery). In the summary tables, this approach is referred to as ‘new anticancer PFS supplementary analysis’.

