3.1 Power for analysis of key secondary variables

No power calculation has been performed for the key secondary variables.

4 Change to protocol specified analyses

Not applicable

5 Appendix

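### Rule G in SAP 2.5.4 omits the biopsy exclusion stated in 2.5.6, and the SAP does not clearly provide the Protocol 12.4.4 PFS analysis that ignores both missed visits and new therapy

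*SAP*

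**What the plan says.** **Rule G.** In SAP Table 2.5-1, situation G censors a patient who starts new anticancer therapy, cross-over or re-treatment before central progression, at the last adequate tumor assessment beforehand. Where there is none after baseline, SAP 2.5.4 says: "If no post-baseline assessments are available (before an event or a censoring reason occurred) then the date of randomization will be used". New anticancer therapy is then defined by a list. For procedures after randomization it has two items: any radiotherapy, and "Procedures (including surgery) with indication of Underlying disease in Concomitant non-drug therapies and interventions eCRF page".

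**Biopsies.** The SAP mentions them once in this context, in 2.5.6, in the definition of the 'new anticancer' supplementary analysis: "not counting biopsies as a new antineoplastic surgery".

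**Sensitivity analysis.** Protocol 12.4.4 describes a single analysis that counts progression or death "regardless of whether the patient had missing scheduled visits, treatment discontinuation for toxicity, or new anticancer treatment started without progression". The SAP has these analyses on the same subject:
- 'Actual event' (2.5.6): "including events whenever they occur, even after two or missing tumor assessments".
- 'Backdating' (2.5.6): re-dates events that follow missed assessments.
- 'New anticancer' (2.5.6): "including events that occur after the start of new antineoplastic therapy if no PFS event is observed prior".
- SAP 2.5.1, on events after new therapy: a "sensitivity analysis will be conducted that considers such events as PFS events for the primary analysis provided central review of tumor assessments continues".

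SAP 2.5.5 adds only analyses by eCRF strata, without strata, and with covariates. SAP Section 4, "Change to protocol specified analyses", is marked not applicable.

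**The concern.** Rule G helps decide which events count in the primary endpoint of an open-label trial. The test that a programmer will apply is an indication field completed at the site. A diagnostic biopsy is not therapy, so censoring for it has no place in the hypothetical strategy of SAP 2.5.3, which concerns new anti-neoplastic therapy. Stating the exclusion in one analysis and leaving it out of the primary definition also invites the inference that the primary analysis does not exclude biopsies.

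The second limb concerns events that follow both two or more missed scans and a new therapy. Informative censoring is most plausible there. The Protocol specified an analysis that counts such events, and a reader of the SAP cannot tell whether one will be run.

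**Working it through.** **Design figures.** Inputs from SAP Section 3: hazard ratio 0.50, one-sided 2.5%, 90% power, 2:1 allocation, 99 events, control median 15 months.
- Events = (1.960 + 1.282)² / [(2/3)(1/3)(ln 0.5)²] = 10.51 / 0.1068 = 98.4, rounded up to 99, as stated.
- Power at 99 events: √(99 × 2/9) = 4.690; 0.693 × 4.690 − 1.960 = 1.291, which gives 90.2%.
- Critical hazard ratio = exp(−1.960 / 4.690) = 0.658, as stated. The median difference is 15 / 0.658 − 15 = 7.8 months, as stated.

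These depend on the event count, the assumed hazard ratio, alpha and allocation. None depends on the wording of rule G or on a supplementary analysis.

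**Limb 1, the texts compared.**
1. Rule G's procedure test has two conditions: the procedure is after randomization, and its eCRF indication is the underlying disease. A tumor biopsy can satisfy both.
2. The biopsy clause in 2.5.6 sits in an analysis that counts events after new therapy anyway. Whether a biopsy is new therapy changes almost nothing there. It would matter in the primary analysis, where it is absent.
3. A biopsy that met the test would therefore censor primary PFS at the preceding adequate scan, or at randomization if none had been done after baseline. Under the censoring reasons in 2.5.6 it would be tabulated as new cancer therapy.
4. The primary and 'new anticancer' analyses would then differ in the definition of new therapy as well as in the censoring rule, so comparing them would not isolate the rule.
5. The key secondary endpoints do not refer to this list. ORR (2.6.1) speaks of additional anti-neoplastic therapy or surgery; time to deterioration (2.6.3) gives no list.

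**Limb 2, the texts compared.** The Protocol analysis sets aside three things.
1. Discontinuation for toxicity: already ignored in the primary analysis (SAP 2.5.3), so there is no gap.
2. Missed visits (situation D of Table 2.5-1): addressed by 'actual event' and 'backdating'.
3. New anticancer treatment (situation G): addressed by 'new anticancer' and by the 2.5.1 analysis.

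What is left open is whether any analysis sets aside D and G together. The opening words of 'actual event' are general enough to do so. The rest of that item explains only the missed-scan rule, and a separate item deals with new therapy. Both readings are possible.

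**Effect on the hazard ratio.** The documents give no number of biopsies, missed scans or new-therapy starts, so neither size nor direction can be calculated.

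**The case against.** On biopsies, the procedure list stands under a heading about new anti-cancer procedures, and a diagnostic biopsy is not one. The 2.5.6 clause can be taken as the sponsor's general convention, written in an odd place. The Protocol schedules no biopsy after randomization: Ki67 comes from specimens required for eligibility (8.1.2), and Tables 8-3 and 8-4 list none. Only unscheduled biopsies coded to the underlying disease are at issue, and nothing shows that any exist. All of this stands and narrows the point. It does not remove it, because the operational test is the eCRF indication and the heading is not a programmable criterion.

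On the sensitivity analysis, Protocol 12.4.3 leaves the detail of censoring to the SAP, and 12.4.4 lets the SAP specify further analyses. If the general opening of 'actual event' governs, the SAP already delivers the Protocol analysis, and the entry in Section 4 is no fault on this account. Each rule is in any case examined separately. This also stands. A reader might infer that the SAP dropped the Protocol analysis, or that no SAP analysis counts an event after both missed scans and new therapy. The text does not support that; it supports only that the matter is unclear. Leave to specify further analyses is not leave to omit the one described.

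A reader might also infer that the primary hazard ratio is biased. The documents show no such effect.

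**Conclusion.** Both limbs hold in limited form. First, the primary censoring definition lacks an exclusion that the SAP states elsewhere, so an unscheduled biopsy coded to the underlying disease could censor a patient contrary to the apparent intent. Second, the SAP does not make clear that it provides the Protocol 12.4.4 analysis, and it records no departure.

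The effect on the hazard ratio cannot be determined. That it is probably small is a judgment, resting on the absence of scheduled biopsies and on procedure use not being both unbalanced between arms and linked to progression. The 99 events, the 90% power and the critical hazard ratio of 0.658 are unaffected. The change should be made because it concerns the primary endpoint and costs little; the validity of the primary test does not hang on it.

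**What to change.** 1. In SAP 2.5.4, exclude biopsies and other purely diagnostic procedures from rule G. Classify them from the eCRF procedure terms before database lock, without treatment codes. Use that one definition of new anticancer therapy in 2.5.6 and for ORR and time to deterioration.
2. Add one PFS analysis by central review on the full analysis set with neither situation D nor situation G censoring, as Protocol 12.4.4 specifies, or state that 'actual event' is that analysis. Keep the single-rule analyses. If neither is done, record the departure in SAP Section 4.

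The cost is a clause in 2.5.4, cross-references, classification of a short list of procedure terms, and at most one extra Cox and Kaplan-Meier run. Sample size, alpha and visits do not change.

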2.5.5 Sensitivity analyses

If there is a high rate of discrepancy ($\geq 10\%$) between the strata classifications constructed using the electronic Case Report Form (eCRF) data and those obtained from the Interactive Response Technology (IRT), a sensitivity analysis will be performed for PFS per central assessment in which a stratified Cox regression model will be used to estimate the treatment hazard ratio and the associated 95% confidence interval based on the eCRF-derived strata. No other inferential statistics will be provided.

In addition, the hazard ratio and 95% confidence interval for PFS as per central assessment will also be obtained from an unstratified Cox model.

Finally, as sensitivity analyses performed in the FAS, the hazard ratio and 95% confidence interval for PFS per blinded independent central review will be obtained from:

- A stratified (using the randomization stratification factors) and covariate adjusted Cox model including covariates at baseline: Age (<65 years vs. ≥ 65 years), Gender, Race, Tumor burden at baseline, CgA, and SSTR tumor uptake score per central review. See [Section 2.2.3](#) for more detailed definition of involved covariates. Time since diagnosis or metastasis will be taken as continuous variables in the model. All covariates will be included in the model regardless of their observed significance (p-value for given covariate).

2.5.6 Supplementary analyses

As supplementary analyses, PFS as per local review will be analyzed using a stratified Cox model, with the same analysis conventions as the primary efficacy analysis, and the treatment effect will be summarized by the hazard ratio with its 95% confidence interval. Kaplan-Meier curves, medians and 95% confidence intervals of the medians will be presented for each treatment group.

In addition, the primary efficacy endpoint will be summarized based on the data obtained below to assess different censoring mechanisms. Kaplan-Meier estimate of median PFS along with 95% confidence intervals, and hazard ratio and corresponding 95% confidence interval obtained using the Cox proportional hazards model will be provided. No other inferential statistics will be provided.

- Using the primary analysis source (i.e., central review using RECIST 1.1 criteria) on the FAS and including events whenever they occur, even after two or missing tumor assessments. The rule to determine number of missing tumor assessments is based on

the time interval between the date of last adequate tumor assessment and the date of event (see [Section 5.5](#)). If the interval is greater than twice the protocol-specified interval between the tumor assessment and two times the protocol-allowed time window around assessments, then the number of missing assessments will be two or more. In the summary tables, this approach is referred to as ‘actual event PFS supplementary analysis’.

- Using the primary analysis source (i.e., central review using RECIST 1.1 criteria) on the FAS and backdating events that occurred after missing one or more tumor assessments (i.e., if progression/death is observed after one or more missing tumor assessments, it is considered as an event at the date of the next scheduled assessment following the last adequate tumor assessment. In the summary tables, this approach is referred to as ‘backdating PFS supplementary analysis’).
- Using the primary analysis source (i.e., central review using RECIST 1.1 criteria) on the FAS and including events that occur after the start of new antineoplastic therapy if no PFS event is observed prior to the start of new antineoplastic therapy (not counting biopsies as a new antineoplastic surgery). In the summary tables, this approach is referred to as ‘new anticancer PFS supplementary analysis’.

For these supplementary analyses, all analyses will be conducted using stratified Cox proportional hazards model. If there are not enough events in all strata, the analysis will be conducted using an unstratified Cox proportional hazards model.

Additionally, the following analyses will be performed:

- Timing of all tumor assessments according to RECIST 1.1 will be depicted graphically, separately for central radiology and investigator/local radiology and displaced by treatment group.
- Comparison of PFS event type/censor between local radiology review and central radiology assessment
- Number of participants with a PFS event and number of participants censored for the PFS analysis will be summarized. In addition, a summary of reasons for PFS censoring will be provided by treatment group. These summaries on censoring reasons will be produced for PFS by investigator radiology and central radiology.

Subgroup analyses for the primary endpoint

If the primary analysis is statistically significant, subgroup analyses to assess the homogeneity of the treatment effect across demographic, and baseline disease characteristics will be performed. Please refer to [Section 2.2.3](#) for detailed subgroup definitions.

For each of the subgroups, the following analyses will be performed:

- Median Kaplan-Meier estimates of the survival distribution of PFS
- Hazard ratio with 95% CI using unstratified Cox proportional hazards model.

Efficacy analyses in subgroups are intended to explore the consistency (homogeneity) of treatment effect. Forest plot (including sample size/number of events and HR with 95% CI) will be produced to graphically depict the treatment effect estimates in different subgroups. No inferential statistics (p-values) will be produced for the subgroups.

Censoring pattern of PFS

The number of patients censored for the PFS analysis will be summarized. In addition, a summary for PFS censoring will be provided by treatment group based on the following reasons:

1. Ongoing without event
2. New cancer therapy added
3. Lost to follow-up
4. Withdrew consent
5. Adequate assessment no longer available
6. Event after ≥ 2 missing tumor assessments

The PFS censoring are defined in the following way:

If the time interval between the last adequate tumor assessment date and the earliest of the following dates is smaller or equal to interval of 2 missing tumor assessments:

1. Analysis cut-off date
2. Start date of further anti-neoplastic therapy
3. Date of consent withdrawal
4. Visit date of study treatment discontinuation or end of post-treatment follow-up discontinuation due to lost to follow-up

Then the PFS censoring reason will be:

1. ‘Ongoing’
2. ‘New cancer therapy added’
3. ‘Withdrew consent’
4. ‘Lost to follow-up’

If the time interval is larger than the interval of 2 missing tumor assessments with no event observed, then the PFS censoring reason will always default to ‘Adequate assessment no longer available’. If the time interval between the last adequate tumor assessment and the PFS event date is larger than 2 missing tumor assessments, then the patient will be censored and the censored reason will be ‘Event documented after two or more missing tumor assessments’.

These summaries on censoring reasons will be produced for PFS by central review and investigator using RECIST 1.1.

Waterfall plot to depict anti-tumor activity

Waterfall graphs will be used to depict the anti-tumor activity. These plots will display the best percentage change from baseline in the sum of diameters of all target lesions for each patient. Only patients with measurable disease at baseline will be included in the waterfall graphs. Special consideration is needed for assessments where the target lesion response is CR, PR or SD, but the appearance of a new lesion or a worsening of non-target lesions results in an overall lesion response of PD. As a conservative approach, such assessments will not be considered for display as bars in the graph, since the percentage change in the sum of diameters of target lesions reflects the non-PD target lesion response, but the overall lesion response is PD. A patient with only such assessments will be represented by a special symbol (e.g. *) in the waterfall graph. Assessments with “unknown” target lesion response and assessments with unknown overall response will be excluded from the waterfall plots. Patients without any valid assessments will be completely excluded from the graphs.

The total number of patients displayed in the graph will be shown and this number will be used as the denominator for calculating the percentages of patients with tumor shrinkage and tumor growth. Footnote will explain the reason for excluding some patients (due to absence of any valid assessment).

All possible assessment scenarios are described in [Table 2.5-2](#).

Table 2.5-2 Inclusion/exclusion of assessments used in waterfall graph

Criteria for inclusion/exclusion				Possible sources of contradictions	
Case	Target response	Overall lesion response	Include in waterfall?	Non-target response	New lesion?
1	CR/PR/SD	PD	Yes but as * only	PD	any
2	CR/PR/SD	PD	Yes but as * only	any	Yes
3	UNK	UNK or PD	No	any	any
4	CR/PR/SD	UNK	No	UNK	No
5	CR/PR/SD	CR/PR/SD	Yes as a bar	SD/IR	No
6	PD	PD	Yes as a bar	any	any

Concordance analysis of PFS using RECIST 1.1

Cross-tabulation of ‘PFS by central review’ vs ‘PFS by investigator’ by PFS event type (i.e., ‘death’, ‘PD’, ‘censor’ for each of the two sources resulting in a 3 by 3 table) and by treatment will be constructed to investigate discordance between the two sources on a patient-by-patient basis (see [Table 2.5-3](#)). Discordance rate between central radiology and investigator will be calculated and presented as % as follows: $100 * (n_{13} + n_{23} + n_{31} + n_{32}) / N$ by treatment group.

Table 2.5-3 Comparison of PFS using RECIST 1.1 between central review and investigator

Central review PFS result

Investigator PFS	Death	PD	Censor
Death	n ₁₁	n ₁₂	n ₁₃
PD	n ₂₁	n ₂₂	n ₂₃
Censor	n ₃₁	n ₃₂	n ₃₃

A cross-tabulation will be produced displaying the PFS timing for the local investigators' assessment compared to the central review assessment (see [Table 2.5-4](#)). For progression assessments, the frequency and percent of subjects with complete agreement, progression later, progression earlier, and cases where progression was called by one method and censored by the other will be displayed. Similarly, if censoring was recorded, the frequency and percent of subjects with complete agreement, censoring called later, censoring called earlier, and cases where censoring was called by one method and progression was called by the other method will be displayed.

Table 2.5-4 Comparison of PFS event times using RECIST 1.1 between central review and investigator assessments

Investigator	Central review	Treatment group (N=xxx)			
		Same time n (%)	Central review after investigator n (%)	Central review before investigator n (%)	Total
PD	PD	xx (xx.x)	xx (xx.x)	xx (xx.x)	xx (xx.x)
Death	Death	xx (xx.x)	0	0	xx (xx.x)
Censor	Censor	xx (xx.x)	xx (xx.x)	xx (xx.x)	xx (xx.x)
PD	Censor	xx (xx.x)	xx (xx.x)	xx (xx.x)	xx (xx.x)
PD	Death	0	xx (xx.x)	0	xx (xx.x)
Death	PD	0	0	xx (xx.x)	xx (xx.x)
Death	Censor	0	0	xx (xx.x)	xx (xx.x)
Censor	PD	xx (xx.x)	xx (xx.x)	xx (xx.x)	xx (xx.x)
Censor	Death	0	xx (xx.x)	0	xx (xx.x)
Total		xx (xx.x)	xx (xx.x)	xx (xx.x)	xx (xx.x)

Cross-over

PFS based on investigator assessment may be performed on the crossover set, if the number of PFS events will allow to perform such analysis. PFS will be defined as the time from the day of the first dose of crossover Lutathera therapy to the date of the first documented disease progression according to RECIST 1.1 as per investigator assessment, or death due to any

cause. Kaplan-Meier curve, median and its corresponding 95% CI of the survival distribution of PFS will be presented.

